3.2.2 Control Arm Condition

All control arm activities may be conducted virtually.

Participants randomized to the control arm will receive:

Digital Health Intervention Standard-of-Care: The control arm version of the HealthMPowerment DHI platform includes Study timeline and Calendar features and all educational content in the Resource Center.

4.0 TRAINING

All training will be conducted virtually or in-person.

4.1 Research Staff Trainings

Any current or future project staff having study-related contact with participants will be required to complete Good Clinical Practice (GCP) and Human Subjects Research training for the responsible conduct of research and the requirements of maintaining privacy and confidentiality. Training for all research staff includes (but is not limited to): an overview of the study; study procedures and human subjects' issues (informed consent process, confidentiality); a demonstration of all technology components (e.g., screening survey, HMP application); methods for establishing comfort with the sensitive issues that may arise; quality management; confidentiality; and reporting of adverse events. Research staff includes the project manager, PIs, and research assistants.

PrEP navigators are not involved in the assessment of study specific outcomes or patient consent. However, given that they are retained by the study and have direct participant interactions, PrEP navigators will complete all required Human Subjects Research and GCP trainings as well as PrEP Navigator Training (Section 4.3).

Clinic staff will not be responsible for assessing patient eligibility nor conducting informed consent or administering any aspect of data collection or intervention delivery. In general, clinic staff will not have access to data other than what they have previously been granted access to through their professional appointment and duties. Some clinics may opt to securely upload records from consenting participants enrolled at their clinic, rather than providing study staff direct access to these records. In this case, study staff will provide a list of consented, enrolled participants from that site to the designated clinic staff via secure, password protected files. All clinics will be asked to participate in an introduction to STARR-NC study procedures training and PrEP training (Section 4.2).

4.2 Clinic Training

Prior to study implementation, representatives from participating clinics will have completed two trainings: introduction to STARR-NC study procedures and introduction to PrEP.

STARR-NC Study Procedures Training: Clinics will select staff to attend study procedure trainings including those who interact with clinic patients who might be eligible for the study (e.g. clinical personnel, clinic leadership, laboratory, front-desk staff). Study procedure trainings will focus on building capacity to ensure that clinic staff can:

- Answer basic patient questions about study objectives and refer patients to the STARR-NC study staff.
- Understand the study timeline and the timeline for when standard of care HIV/STI testing should occur in line with current CDC clinical guidelines ³¹.

- Know when and how to contact STARR-NC study staff with questions or concerns related to study implementation or participant follow-up.

PrEP Training: As described in Section 1.0, there are currently no PrEP services offered at any of the participating clinics. While all participating clinics have expressed interest in expanding access to PrEP for their patients, the timing and resource capacity of each clinic to begin offering PrEP on-site is outside of the scope of this project. PrEP capacity includes everything from on-site provision of PrEP, robust PrEP referral strategies, or PrEP provider knowledge to help answering basic questions regarding PrEP effectiveness and eligibility for patients who express interest in PrEP. As a first step in building PrEP capacity at the clinic level, the North Carolina HIV Training & Education Center (NC HTEC) will provide PrEP training to all participating clinics. This standardized program will provide all participating clinics the same PrEP awareness and knowledge training regardless of each individual clinic's intention or ability to launch clinic-embedded PrEP clinics. Delivering the same training across all clinics provides clinic staff common messaging about PrEP which could help limit this potential source of site-level variation in the context of the study. PrEP training content areas will include educational and skill building to:

- Explain how PrEP protects against HIV infection.
- Distinguish among PrEP, PEP, and U=U.
- Outline criteria that would make a client eligible for PrEP.
- Describe the components of PrEP service delivery.
- Identify resources to help patients prepare for, initiate, and persist on PrEP.

4.3 PrEP Navigator Trainings

PrEP navigators will complete all trainings described in Sections 4.1 and 4.2. In addition, PrEP navigators will complete structured and hands-on training using resources developed by PrEP-focused organizations and initiatives, including:

- PleasePrEPMe
- AIDS Education & Training Center Program National Coordinating Resource Center
- Centers for Disease Control and Prevention
- National Minority AIDS Council
- U.S. National Library of Medicine
Centers for Disease Control and Prevention National Prevention Information Network

Drawing from the above trainings, PrEP navigators will be trained to conduct the following:

- All study staff and clinic competencies as described in Sections 4.1 and 4.2 above.
- Facilitate linkage to PrEP services, including assisting participants with identifying/connecting with a PrEP provider and completing appropriate referral paperwork as needed.
- Support completion of Medicaid enrollment assistance and drug assistance programs, as appropriate.
- Recommend and discuss resources and strategies for supporting PrEP medication adherence and maintenance.
- Identify and recommend community resources that are culturally sensitive to communities at highest need for PrEP.
- Stay informed about current HIV/AIDS trends, prevention efforts, and strategies.
- Demonstrate cultural humility, understanding, awareness, and respect for diversity among study participants.

5.0 SELECTION AND ENROLLMENT OF STUDY PARTICIPANTS

5.1 Participant Inclusion Criteria

RCT eligible participants must: (1) report sexual activity with a male in the past 12 months; (2) received HIV testing within 90 days pre-enrollment and not known to be HIV-positive at screening/enrollment by self-report (3) age 18-39 years; (4) have daily smartphone access; (5) be English speaking; and (6) deny current PrEP use (i.e. has not taken oral PrEP or received injectable PrEP within the last 3 months).

Qualitative interview (clinic patient participants) must be enrolled in the study and complete their Baseline study visit activities and at least one follow-up study time point (3 and/or 6-month visit). We will interview up to 50 patient participants. Participants will be purposively sampled to ensure a diversity in areas such as PrEP initiation status, recruitment clinic, age, sex, and race/ethnicity.

Qualitative interviews (clinic staff/providers/relevant stakeholders): We will conduct qualitative interviews with a purposively selected sample of up to 50 clinic staff, providers and other relevant stakeholders for PrEP provision. Interviewees will be purposively sampled to ensure a diversity of clinic roles and relationship to PrEP provision services and referrals, diversity in leadership level, and representation across all participating clinics.

5.2 Participant Recruitment

The study team and clinic representatives will meet as needed to troubleshoot any clinic-specific or cross-clinic recruitment challenges, as well as share successes.

Venue-based recruitment at participating STI clinics: Ads (e.g. posters, one-pagers) and business cards/palm cards with scannable QR codes will be posted throughout the clinic waiting areas, bulletin boards, patient rooms, etc. The study will also be promoted through word of mouth via the clinic health professionals, administrative staff, and community outreach personnel. Clinic and study staff may also bring recruitment materials to community-based events they attend on behalf of the clinic (e.g. health fairs, blood drive) with information about the study and encouraging persons to seek STI services at their local STI clinic.

Primary recruitment materials: Scannable QR codes will lead to a study landing page and online screener, which allows people to learn about the study discretely if they do not wish to carry study-related materials on their person. Each county will be assigned an individualized QR code so that study staff can recognize which county each completed screener is associated with. If multiple collaborating clinics exist within one county, the participant will self-report from which clinic they engaged with recruitment materials. We will work with clinic staff and our Community Advisory Board to develop a comprehensive recruitment portfolio, reviewing messages, imagery, tone and dissemination modalities. All recruitment materials will be reviewed and approved by the IRB prior to use.

Social media promotion: In addition to clinic-based recruitment, we will also work with each clinic to establish a social media recruitment plan. To maintain consistency across clinics, the intention of the social media promotion is to increase visibility of the clinic to the target population and encourage our population of interest to seek sexual health services through the collaborating clinics.

5.3 Procedures to Minimize Fraudulent Participation

Study ads and the initial screener will not indicate full, explicit eligibility criteria and will de-emphasize incentives as to minimize fraudulent responses. UNC study staff will verify eligibility prior to full study enrollment.

5.4 Screening for Eligibility

County-specific QR codes are used to link potential participants to a study pre-screening assessment. Patients will be asked for consent to screen and then complete the pre-screening questionnaire independently of study or clinic staff. Prospective participants that complete the eligibility assessment questions will receive a small incentive valued at approximately \$5. The pre-screening assessment will explain the name, sponsor, funder, and the purpose of the study and assess key eligibility criteria (Section 5.1) and collect basic demographics. Participants who are not eligible based on screening criteria, duplicate entries, or choosing not to proceed, will be thanked, and rerouted to a public webpage (e.g., Google). Prospective participants will be asked permission for study staff to contact them and to provide preferred contact information (preferred name, pronouns, phone number, email, preferred time for phone, text or email contact).

5.5 Informational Video

After providing contact information, prospective participants who are found to be eligible thus far, will be routed to a brief online video outlining the purpose of the study, participant activities, data collection, and timeline of participation. Participants may view the video immediately after pre-screening or at a time most convenient to them.

5.6 Informed Consent

Participants have the choice to complete a self-guided electronic informed consent following the informational video prior to enrollment, or to complete a staff-guided electronic informed consent (via HIPAA-compliant videoconferencing platform or phone call) prior to enrollment. All participants will be asked to complete comprehension questions to ensure they adequately understand the research, risks, and benefits prior to providing an electronic signature (Section 15.5).

5.7 HIPAA Authorization

All prospective participants who complete Informed Consent will be required to review and sign a HIPAA release form, approved by the UNC IRB, to facilitate study access to test results specific to study outcomes and PrEP eligibility and medical records related to receipt of PrEP-related services. The release form specifies the scope of results/records that will be accessed and the timeframe over which research staff would be able to access this information.

5.8 Participant Randomization

Participants will be randomized 1:1. Randomization procedures are automated through the study database. Randomization is completed after a participant has completed informed consent and their Baseline survey. Participants will be informed by study staff of their study condition assignment during their onboarding appointment. The study onboarding appointment is tailored to the study arm condition they are assigned (Figure 2).

Study staff are trained to follow similar protocol for scheduling, enrollment, and follow-up regardless of arm which includes the use of IRB-approved guides for participant communications and specified standard operating procedures for participant outreach mode, timing, and frequency. Communication attempts will be tracked in a communication log for prospective and enrolled persons. PIs and the study monitor will be able to see the records for all those who complete screening and could assess whether there is differential communication efforts or enrollment by randomization condition.

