6.1 Study onboarding appointment and baseline assessment

[figure not shown]
All participants will complete an onboarding appointment via phone or HIPAA-compliant videoconferencing platform. Participants will be considered enrolled and be eligible for the enrollment completion incentive once the below activities are complete:

- Informed consent and HIPAA authorization. Receipt of a unique access link to complete their Baseline CASI survey capturing PrEP use history, sexual behaviors, demographics, and determinants of PrEP use (access to care, perceived HIV risk, social support, perceived discrimination, mental health, substance use, and PrEP decision making). The CASI survey is self-administered via secure HIPAA-compliant platform (e.g. RedCap) and participants can complete the survey on their personal device with internet, wi-fi or mobile data. The survey saves after every page thus participants can return to complete the survey if their connection is disrupted or for any other reason.
- Randomized to study condition.
- Receipt of a unique access code and directions to download their free designated version (intervention or control) of the HMP study app from either the Google Play or Apple store.
- Creating their unique HMP account profile and log-in; touring the app features.

The onboarding appointment for intervention participants will also include being connected to their assigned PrEP navigator.

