6.4 Follow-up study assessments

Follow-up study assessments will be conducted for all participants, including standard of care repeat HIV/STI testing³¹ and repeat self-administered CASI survey assessments, with the number of follow-up assessments dictated by timing of enrollment. The baseline questionnaire is distributed after a participant completes informed consent and before they are randomized. If the participant does not complete Informed Consent, HIPAA Authorization, the baseline questionnaire and baseline HIV status verification within 45 days of completing the screening questionnaire, the participant must re-screen to assess eligibility.

The follow-up period (described as the post-randomization phase) begins once participants have been randomized to a study condition. Randomization will occur once participants have connected with study staff for their onboarding appointment. An overview of the pre and post randomization assessments conducted in each study phase are described in Tables 2.1 – 2.3.

A subset of participants will be asked to complete a brief CASI survey pertaining to PrEP uptake and/or persistent use and self-reported STI or HIV testing outcomes at 12-months if this follow-up interval falls within the allowable data collection timeframe based on when a person was enrolled (see Section 17.0 Timeline). The study windows for each follow-up time

Table 2.1: Participant Assessment Timeline

| Pre-Randomization | | | |
|--|----------|-----------|------------------------------|
| Study Activity | Day Open | Day Close | Study Window Duration (days) |
| Screening Questionnaire | 0 | 45 | 45 |
| Informed Consent + HIPAA Authorization | 0 | 45 | 45 |

Table 2.2: Participant Assessment Timeline for Participants Followed 6 -12 Months

| Post-Randomization | | | |
|--|----------|-----------|------------------------------|
| Study Activity | Day Open | Day Close | Study Window Duration (days) |
| App Account Generation | 0 | 0 | 1 |
| Baseline STI Result Abstraction ¹ | 0 | 89 | 89 |
| Baseline HIV Result Abstraction ² | 0 | 45 | 45 |
| 3M Survey | 90 | 165 | 75 |
| 3M DBS | 75 | 165 | 90 |
| 3M HIV/STI Result Abstraction ¹ | 90 | 165 | 75 |
| 6M Survey | 166 | 196 | 30 |
| 6M DBS | 166 | 211 | 45 |
| 6M HIV/STI Result Abstraction ¹ | 166 | 276 | 110 |
| 12M Survey ³ | 365 | 440 | 75 |
| Qualitative Exit Interview ³ | 90 | 276 | 186 |

Table 2.3: Participant Assessment Timeline for Participant Followed for 3 Months

| Post-Randomization | | | |

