8.4 Participant Withdrawal

Enrolled participants are free to withdraw from participation in the study at any time and for any reason upon request. A study stop CRF will be completed for participants who request withdraw from the study. No further data collection will occur following completion of the study stop CRF.

An investigator may withdraw a participant from the study for the following reasons:

- a) If any clinical adverse event (AE), serious adverse event (SAE), laboratory abnormality, or other medical condition or situation – related or unrelated to the study – develops after enrollment such that continued participation in the study would not be in the best interest of the participant.
- b) If a patient presents a safety risk to the research staff.
- c) If their participation in the study is disruptive to the study or the clinic.
- d) If the participant receives an HIV diagnosis (see section 8.3).
- e) They intentionally violate study procedures, including fraudulent engagement with study screening or DHI-based survey completion.

The reason for any participant's discontinuation or withdrawal from the study will be recorded on the study stop CRF.

Furthermore, study staff may use their professional discretion not to enroll a prospective participant for reasons b through e, listed above.

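### The moment of randomisation is described in two unreconciled ways, and a person counts as enrolled only after later steps, so randomised people can drop out of the enrolled count once staff know the arm

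*Combined protocol and SAP*

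**What the plan says.** Section 5.8 states that "Randomization procedures are automated through the study database" and that "Randomization is completed after a participant has completed informed consent and their Baseline survey". Staff then tell the participant the assignment at onboarding, and "The study onboarding appointment is tailored to the study arm condition they are assigned". The note to Figure 2 also separates automated assignment from disclosure at onboarding; the figure itself is not available.

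Section 6.4 gives a different anchor: "Randomization will occur once participants have connected with study staff for their onboarding appointment". It adds that follow-up "begins once participants have been randomized to a study condition", and the survey and dried-blood-spot windows count from that date.

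Section 6.1 defines enrolment: "Participants will be considered enrolled and be eligible for the enrollment completion incentive once the below activities are complete". The listed activities include randomisation, followed by app access and creation of the app account. For the intervention arm, the link to the navigator is also made at onboarding.

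Section 8.4 says that "study staff may use their professional discretion not to enroll a prospective participant for reasons b through e". It sets no point in the sequence after which this no longer applies.

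As safeguards, Section 5.8 describes similar staff procedures in both arms, approved communication guides, operating procedures for outreach, and a communication log. It adds that the investigators and the study monitor "could assess whether there is differential communication efforts or enrollment by randomization condition".

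**The concern.** In an individually randomised trial, the people compared should be the people randomised. If the arm is assigned first and enrolment is completed later, by staff who know the arm and through an appointment whose content differs by arm, the enrolled groups may no longer be the randomised groups. Those who drop out in between are likely to be less engaged, and so less likely to start PrEP. Leaving them out raises apparent uptake, and more so in the arm that loses more.

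This bears on the go/no-go decision: milestone 5 in Section 11.0 rests on the difference in 3-month uptake, with 7.5 percentage points as the reference value. A gap between allocation and onboarding would also start the assessment windows before the app and navigator are available.

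**Working it through.** **Order of steps.** Section 5.8 requires consent and the baseline survey before randomisation but does not say how soon after them it happens. Section 6.4 also puts the baseline questionnaire first, then requires contact with staff for onboarding. The sequence survey, staff contact, automated randomisation, disclosure, app account fits 5.8, 6.1 and 6.4. The sequence survey, automated randomisation, wait, onboarding fits 5.8 but not 6.4. Nothing in 5.8 rules the second one out.

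Tables 2.2 and 2.3 put generation of the app account on post-randomisation day 0 only. Because 6.1 makes account creation an enrolment step, this suggests same-day randomisation and onboarding, but only by inference: the row does not mention onboarding.

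**Who can be lost after allocation.** On either sequence, randomisation precedes app access and account creation, so a randomised person who does not finish them is not enrolled under 6.1. On the first sequence the exposure is confined to one appointment; on the second it lasts as long as the wait. Section 5.8's reference to enrolment by randomisation condition makes sense only if allocation can precede completed enrolment.

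**Effect on the estimate.** The plan states no figure to reproduce. From Section 9.1: control uptake 2.5% and a difference of 7.5 points, so 10% in the intervention arm. Assumed: a share L of each arm is lost after allocation, none of the lost start PrEP, and the lost are left out of the analysis. Then

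uptake among those retained = uptake among all randomised / (1 − L).

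| Assumed loss, intervention / control | True uptake | Apparent difference |
|---|---|---|
| 15% / 5% | 10% vs 2.5% | 0.10/0.85 − 0.025/0.95 = 11.8% − 2.6% = 9.1 points |
| 20% / 10% | 10% vs 2.5% | 0.10/0.80 − 0.025/0.90 = 12.5% − 2.8% = 9.7 points |
| 5% / 15% | 10% vs 2.5% | 0.10/0.95 − 0.025/0.85 = 10.5% − 2.9% = 7.6 points |
| 10% / 10% | 10% vs 2.5% | 0.075/0.90 = 8.3 points |
| 15% / 5% | 5% in both | 0.05/0.85 − 0.05/0.95 = 0.6 points |
| 20% / 10% | 5% in both | 0.05/0.80 − 0.05/0.90 = 0.7 points |

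The equal-loss row shows that part of the inflation comes from leaving non-starters out at all, not from the imbalance. If the lost had the same uptake as those retained, the estimate would not move.

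**Effect of a gap on the windows.** The 3-month dried-blood-spot window opens on day 75 after randomisation and the survey window on day 90. An assumed wait of 14 or 28 days for onboarding takes 14/90 = 16% or 28/90 = 31% of the first 90 days, during which the app and navigator are not yet available.

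**HIV-status verification.** Section 5.8 does not require it before randomisation. Section 6.4 requires it within 45 days of screening, failing which the person must re-screen. Table 2.2 lists the abstraction under post-randomisation activities, while footnote 2 counts its 45 days from the screening questionnaire. Section 8.3 says that people found seropositive at verification do not complete enrolment, and Section 9.1 accepts that a small proportion may be randomised before the result is available. These passages do not say how a person already randomised is counted.

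**The case against.** The strongest reply is that there is no contradiction. Section 5.8 gives an order, not an instant, and can be read together with 6.4. That stands: this is an unresolved ambiguity. A reader might also infer that the day-0 app row settles the matter in favour of 6.4. It does not, because it could equally record the issue of an account or access code.

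A reader might infer that allocation concealment is broken. The documents do not support that. Assignment is automated, blocks of 4 and 6 are randomly ordered so that staff cannot foresee the next arm (Section 3.2), and consent and the baseline survey come first on either reading. What remains is selection after allocation.

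Section 8.4 refers to a prospective participant, and no text describes refusing someone already randomised. That is fair, but since 6.1 completes enrolment after randomisation, the term does not clearly exclude such a person. The safeguards in 5.8 are real and mostly prospective; only the comparison by arm is optional.

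Finally, not being enrolled is not the same as being excluded from analysis. Section 9.2.1 compares patients by randomised group, and it is the app-download condition in 9.1 that would leave people out. This also stands: the bias figures need that condition or an equivalent exclusion.

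**Conclusion.** The concern holds as a point about sequence and definitions. The plan does not fix one moment of randomisation, and it lets randomised people fail to become enrolled after staff know the arm. The size is unknown. Under the assumed losses of 15% and 5%, with zero uptake among the lost and the lost left out, 7.5 points would appear as 9.1. With no true effect and 5% uptake in each arm, the bias is about 0.6 points, which is small against 7.5. The reverse imbalance leaves the difference almost unchanged at 7.6.

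A reader might infer that a gap shortens the period over which the primary outcome is counted. It does not: that outcome runs from the index STI clinic visit (Section 9.2.1), which precedes randomisation on either reading, and moving the trigger would not bring navigation closer to that visit. The timing problem concerns the survey and dried-blood-spot windows, which would begin before the intervention is available. The point deserves correction because the remedy is cheap, not because a large bias has been shown.

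**What to change.** - State one trigger in 5.8, 6.1 and 6.4: automated randomisation is run during the onboarding contact, after consent, HIPAA authorisation, the baseline survey and any 8.4 decision not to enrol have been logged.
- Define enrolled, and the target of 336, as persons randomised. The completion incentive can stay tied to finished onboarding under that name.
- State in 8.4 that no discretionary refusal is allowed after allocation.
- Report by arm the number randomised, the number onboarded and the days between, including for anyone already randomised before onboarding. This turns the optional check in 5.8 into a planned one.
- Reconcile the timing of HIV-status verification across 6.4, footnote 2 to Table 2.2, 8.3 and 9.1. Limit any post-randomisation exclusion on that ground to HIV status that predates randomisation, applied in the same way in both arms.

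Moving the trigger shortens the exposure but does not remove it, because the app steps still follow allocation; the new definition deals with the rest of the count. The app-download condition in 9.1 must be made consistent with that definition, or non-completers will be counted and still left out of the analysis.

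The cost is protocol wording and one database trigger, with no new visit, staff or data collection. Reconciling the HIV-status passages takes some further drafting. The downside is that a few randomised non-completers count toward 336.
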